8.4 Analyses

8.4.1 Demographics and Baseline Characteristics

Demographic and baseline characteristics will be summarized for all randomized subjects by treatment group, as randomized, using descriptive statistics.

8.4.2 Efficacy Analyses

The analyses of primary (OS) and secondary (PFS, OS[24]) endpoints will be based on all randomized subjects. Safety summaries will be based on all treated subjects. If superiority in OS is demonstrated, a hierarchical hypothesis testing approach for the secondary endpoint of PFS will be used to preserve a familywise type I error rate at 0.05.

The formal statistical testing for PFS will take place only if OS is statistically significant. Secondary endpoints of OS[24] and OS and PFS in the TMB-high population will be estimated using the Kaplan Meier method.

8.4.2.1 Analyses of Primary Endpoint

The distribution of OS in all randomized subjects will be compared in arms RT + nivolumab and RT + TMZ at the final analysis via a two-sided, log-rank test, stratified by complete resection or partial resection at baseline. The Kaplan-Meier product limit method will be used to estimate the survival curve in each arm including medians and its 95% CI, OS rates at pre-specified time points. The HR and the corresponding two-sided 95% CIs will be estimated in a Cox proportional hazards model with treatment arm as a single covariate stratified by corresponding stratification factor (complete or partial surgical resection at baseline).

8.4.2.2 Analyses of Secondary Endpoints

The comparison of PFS will be based on a two-sided log-rank test stratified by corresponding stratification factor (complete surgical or partial resection at baseline). The details of the testing procedure will be specified in the SAP. OS[24] will be estimated when all censored subjects have had follow-up of at least 24 months. OS and PFS in the TMB-high population will be estimated using the Kaplan-Meier method. Additional details for the analysis of OS[24] endpoint will be included in SAP.

[REDACTED]

[REDACTED]

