The analyses of primary endpoint of OS and secondary endpoints of PFS and OS[24] will be based on all randomized subjects. If superiority in OS is demonstrated, a hierarchical hypothesis testing approach for the secondary endpoint of PFS will be used to preserve a study-wise type I error rate at 0.05. OS[24] will be estimated using Kaplan Meier method. OS and PFS will also be estimated for the TMB-high population.

OS and PFS distribution in all randomized subjects will be compared between treatment groups using a two-sided stratified log-rank test. The hazard ratio (HR) and corresponding two-sided 95% confidence intervals (CIs) will be estimated in a Cox proportional hazard model using treatment as a single covariate stratified by complete or partial resection at baseline.

OS and PFS curves will be estimated using the Kaplan- Meier product-limit method. Median OS and PFS along with the corresponding two-sided 95% CIs using the log-log transformation will be computed.

OS [24] and the corresponding 95% CIs using the log-log transformation will be computed after all subjects have follow-up of at least 24 months. OS and PFS in the TMB-high population will be estimated using the Kaplan-Meier method.

TABLE OF CONTENTS

TITLE PAGE 1

DOCUMENT HISTORY 3

OVERALL RATIONALE FOR THE REVISED PROTOCOL 05 6

SUMMARY OF KEY CHANGES OF REVISED PROTOCOL 05..... 6

SYNOPSIS..... 9

TABLE OF CONTENTS..... 13

[REDACTED] 17

[REDACTED] 18

[REDACTED] 18

[REDACTED] 19

[REDACTED] 20

[REDACTED] 20

[REDACTED] 22

[REDACTED] 22

[REDACTED] 23

[REDACTED] 23

[REDACTED] 23

[REDACTED] 24

[REDACTED] 25

[REDACTED] 25

1.2 Research Hypothesis 25

1.3 Objectives(s) 25

 1.3.1 Primary Objective 25

 1.3.2 Secondary Objectives 25

 1.3.3 Exploratory Objectives 25

[REDACTED] 26

[REDACTED] 26

[REDACTED] 27

[REDACTED] 28

[REDACTED] 28

[REDACTED] 29

2 ETHICAL CONSIDERATIONS 29

 2.1 Good Clinical Practice 29

 2.2 Institutional Review Board/Independent Ethics Committee 30

 2.3 Informed Consent 30

3 INVESTIGATIONAL PLAN 31

 3.1 Study Design and Duration 31

 3.1.1 Screening Phase 33

 3.1.2 Treatment Phase 35

 3.1.2.1 Randomization and Initiation of Treatment 35

 3.1.2.2 Radiotherapy 35

[figure not shown]
[figure not shown]
[figure not shown]
[figure not shown]
[figure not shown]
[figure not shown]

[figure not shown]
[figure not shown]
[figure not shown]
[figure not shown]
 3.1.3 Follow-up Phases 36

 3.1.4 Overall Study Duration 36

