1.3.2 Secondary Objectives

- To compare investigator-assessed PFS of RT + nivolumab versus RT + TMZ
- To estimate the OS rate at 24 months (OS[24]) of RT + nivolumab versus RT + TMZ (final analysis only)
- To evaluate, in newly diagnosed, unmethylated MGMT GBM, any relationship between OS or PFS and TMB in the RT + nivolumab arm compared to the RT + TMZ control.

[REDACTED]

[REDACTED]

[REDACTED]

[REDACTED]

[REDACTED]

[REDACTED]

[REDACTED]

[REDACTED]

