8 STATISTICAL CONSIDERATIONS

8.1 Sample Size Determination

This is a Phase 3, randomized, open label, multicenter study of RT + nivolumab versus RT + TMZ in adult (≥ 18 years) subjects with newly diagnosed GBM subjects with unmethylated MGMT tumors.

Primary objective of the study is to compare the OS of RT+ nivolumab versus RT+TMZ in subjects with newly diagnosed GBM subjects with unmethylated MGMT tumors after surgery.

The sample size for this study is based on the following assumptions:

- 1) OS follows exponential distribution
- 2) Median OS in RT + TMZ arm is 13.0 months (Weller 2009³⁴)
- 3) Hazard ratio (HR) of arm RT + nivolumab vs RT + TMZ is 0.72, translated to median OS improvement of 5.0 months (13.0 months vs 18.0 months for arm RT + TMZ and arm RT + nivolumab, respectively)

At least 390 events (ie, death) provides 90% power to detect a hazard ration (HR) of 0.72 with an overall type 1 error of 0.05 (two-sided). This translates to an observed HR of 0.82 (median OS of 13.0 vs 15.8 months) or less resulting in a statistically significant improvement.

Approximately 550 subjects will be randomized to the two arms (RT +nivolumab vs RT + TMZ) in a 1:1 ratio stratified by complete or partial resection at baseline. Accrual will take approximately 10 months. The total duration of the study from start of randomization to final analysis of OS is expected to be approximately 33 months (10 months of accrual + 23 months of follow-up, Table 8.1-1).

Power calculations were done using East v 6.3.

Table 8.1-1: Key parameters of Sample Size Calculation of OS

Assumptions	Analysis	Goal/Timing (from first subject randomized)	Significant Nominal p-value	Probability for declaring superiority Under HA/H0
$\alpha = 0.05$ Power = 90% Control arm (RT+TMZ) median OS = 13.0 months; Treatment arm (RT + Nivolumab) Median OS = 18.0 months HR = 0.72	Final Superiority	390 OS events/ 33 months	Superiority Observed nominal p-value ≤ 0.05	90%/5%

The PFS, overall survival at 24 months (OS[24]), and OS and PFS in TMB-high patients are secondary endpoints. OS[24] is included as secondary endpoint to evaluate the improvement in long term survival. Only PFS will be tested using a hierarchical testing procedure. (Section 8.4.2).

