4.2.2 Overall Survival at 24 months

Overall survival at 24 months is defined as probability of survival at 24 months based on Kaplan-Meier method. It will be estimated only when minimum follow-up is 24 months or more. In case the minimum follow-up is less than 24 months, but it is judged that data immaturity does not affect interpretability of the results, 24 months OS rate will be provided.

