7.5.1 Overall Survival

7.5.1.1 Primary Analysis

The primary objective of the study is to compare the overall survival between treatment groups in all randomized subjects.

Overall survival will be compared between the treatment groups using stratified log-rank test (5% alpha level), the two-sided log-rank p-value will be reported. The stratified hazard ratio between the treatment groups will be presented along with the 95% CI.

OS will be estimated using the KM techniques. A two-sided 95% CI for median OS in each treatment group will be computed via the log-log transformation method. OS rates at fixed time points (e.g. 12, 18, 24 months, depending on the minimum follow-up) will be presented along with their associated 95% CIs. These estimates will be derived from the Kaplan Meier estimate and corresponding CIs will be derived based on Greenwood formula for variance derivation and on log-log transformation applied on the survivor function. Minimum follow-up must be longer than the timepoint to generate the estimate. In case the minimum follow-up is less than the timepoint, but it is judged that data immaturity does not affect interpretability of the results, the estimate will be provided.

The status of subjects who are censored in the OS KM analysis will be tabulated for each treatment group using the following categories:

- On-study (on-treatment, in follow-up)
- Off-study (lost to follow-up, withdraw consent, never treated)

To examine the assumption of proportional hazards in the Cox regression model, in addition to treatment, a time-dependent variable defined by treatment by time interaction will be added into the model. A two-sided Wald Chi-Square p-values of less than 0.1 will indicate a potential nonconstant treatment effect. In that case, additional exploratory analyses may be performed.

A by-subject listing will be presented including treatment arm, OS, whether the subject was censored, and if censored, the subject’s status.

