7.5.1.4 Subject Follow-Up

The extent of follow-up defined as the time between randomization date and last known date alive (for subjects who are alive) or death date (for subjects who died). It will be summarized descriptively (median, min, max) in months for all randomized subjects.

The currentness of follow-up, defined as the time between last OS contact (i.e., last known date alive or death date) and data cut-off date (defined by last patient last visit date), will be summarized in months by treatment group. Subjects who died and subjects with a Last Known Date Alive on or after LPLV will have a value of '0' for currentness of follow-up. The currentness of follow-up will be categorized into the following categories: 0 days, 1-30 days, 31-60 days, 61-90 days, 91-120 days, 120-150 days, 151 or more days.

Minimum follow-up for OS, defined as the time from cutoff date to last subject's randomization date, will be summarized in months for all randomized subjects.

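### Does the 24-month follow-up rule for OS[24], which the final analysis is expected to miss by about a month, call for a change?

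*Protocol*

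**What the plan says.** OS[24] is a secondary endpoint, the Kaplan-Meier survival probability at 24 months in each arm. Protocol section 1.3.2 ties it to one occasion: "To estimate the OS rate at 24 months (OS[24]) of RT + nivolumab versus RT + TMZ (final analysis only").

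The follow-up condition is worded in three ways:

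- Protocol Synopsis, Analyses: OS[24] "will be computed after all subjects have follow-up of at least 24 months".
- Protocol section 8.4.2.2: "OS[24] will be estimated when all censored subjects have had follow-up of at least 24 months". The same section leaves further detail on OS[24] to the SAP.
- SAP section 4.2.2: "It will be estimated only when minimum follow-up is 24 months or more". Section 7.5.1.4 supplies the definition: "Minimum follow-up for OS, defined as the time from cutoff date to last" subject's randomization.

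Protocol section 8.1 and SAP section 5 put the final analysis at about 33 months, made up of "10 months of accrual + 23 months of follow-up".

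The SAP then deals with shorter follow-up. Under section 4.2.2, if the minimum is below 24 months "but it is judged that data immaturity does not affect interpretability of the results, 24 months OS rate will be provided". Section 7.5.1.1 applies the same allowance to OS rates at fixed times: "but it is judged that data immaturity does not affect interpretability of the results, the estimate will be provided". SAP section 10 shows that this allowance came in with version 3.0. SAP section 7.5.4 states that OS[24] is not tested.

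**The concern.** Taken at face value, the plan assigns a named secondary endpoint to an analysis at which its own condition is not expected to hold: 23 months is less than 24. The Protocol contains no exception, and no later OS[24] analysis is scheduled; Protocol section 3.1.4 only permits further data collection. What rescues the endpoint is a SAP clause that says neither who judges, nor when, nor by what measure of maturity.

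The trial is open-label, so a reader could fear that the 24-month rate would be shown or withheld after the arms had been compared. If that choice could change what the trial concludes, or if the early estimate were seriously imprecise, the clause would need tightening.

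**Working it through.** **Inputs** (Protocol section 8.1, repeated in SAP section 5): 550 subjects, 1:1, so 275 per arm; accrual over about 10 months; exponential survival; control median 13.0 months; HR 0.72; 390 deaths; two-sided alpha 0.05. My assumptions: uniform accrual and, at first, no dropout, since the available text states no dropout rate.

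**1. The plan's own figures.** The Schoenfeld formula gives 390 deaths for 90% power at HR 0.72. The critical HR is exp(−1.96 × 2/√390) = 0.82, which is 13.0 against 15.85 months. Both agree with the plan.

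**2. Timing.** Expected deaths per arm at calendar month T are

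275 × {1 − [exp(−λ(T − 10)) − exp(−λT)]/(10λ)}, with λ = ln 2/median.

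At T = 33:

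- Control, λ = 0.0533: 275 × [1 − (0.2934 − 0.1721)/0.533] = 212.5.
- Nivolumab, λ = 0.72 × 0.0533 = 0.0384: 275 × [1 − (0.4136 − 0.2817)/0.384] = 180.6.
- Total: 393, so the plan's 33 months is reproduced to within half a month.

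Setting the total to 390 and taking T − 10 as minimum follow-up:

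| True HR | T (months) | Minimum follow-up | Potential follow-up under 24 months |
|---|---|---|---|
| 0.72 | 32.6 | 22.6 | 14% |
| 0.82 | 30.8 | 20.8 | 32% |
| 1.0 | 28.4 | 18.4 | 56% |

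The last column is (24 − minimum follow-up)/10.

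**3. How firm the shortfall is.**

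- Assumed dropout enters as η = −ln(1 − annual rate)/12, which replaces λ by λ + η in the exponentials and scales deaths by λ/(λ + η). The 24-month rule is then met at annual dropout of about 2.6% (HR 0.72), 6.0% (HR 0.82) or 10.8% (HR 1.0).
- With no dropout, it is met at a control median of about 13.7, 14.6 or 16.2 months respectively.
- A cutoff at month 34 also meets it. About 400 deaths are expected by then at HR 0.72, which is consistent with a trigger of at least 390.
- Accrual of 8 to 16 months at HR 0.72 gives a minimum of 23.5 down to 19.9 months, so slower accrual widens the gap.

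**4. What early reporting costs.** Under the plan's assumptions S(24) is 0.278 (control) and 0.398 (nivolumab). With full 24-month follow-up the standard errors are √(0.278 × 0.722/275) = 2.70 points and √(0.398 × 0.602/275) = 2.95 points. With staggered entry, Greenwood's variance is S(24)² × ∫ λ/[275 × P(C > t) × S(t)] dt over 0 to 24 months, where P(C > t) is the share with potential follow-up beyond t. At the 390th death:

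| True HR, arm | At risk at 24 months | SE | SE, full 24 months |
|---|---|---|---|
| 0.72, control | 66 | 2.71 | 2.70 |
| 0.72, nivolumab | 94 | 2.96 | 2.95 |
| 1.0, each arm | 34 | 2.93 | 2.70 |

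As an approximate 95% half-width in the control arm, this is 1.96 × 2.71 = 5.3 points at HR 0.72, the same to one decimal as with full follow-up. At HR 1.0 it is 1.96 × 2.93 = 5.7 points.

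At month 33 itself, 55 of 550 subjects (10%) would have entered less than 24 months before. About 19 of them (8 control, 11 nivolumab) would be alive and censored before month 24.

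**The case for a change.** The strongest case for a change is that this is an internal conflict visible without any modelling, and that the SAP settles it by discretion. With no dropout the shortfall grows as the true HR nears 1, so the clause is most likely to be needed when the treatment effect is weak. A sentence in the SAP would remove the discretion cheaply.

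Part of this stands. The decision-maker, the timing and the criterion are unstated, and without dropout a shortfall is likelier than not: at HR 0.72, 24 months was reached in only about 16% of simulated trials.

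The rest carries less weight:

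- The Protocol hands OS[24] detail to the SAP, so the SAP clause is not an unauthorised override. SAP section 7.5.5 speaks of the primary database lock as still to come, which suggests the clause was in place before it.
- Discretion can remove a table row but not the information. Protocol section 8.4.2.1 and SAP section 7.5.1.1 provide the Kaplan-Meier analysis whatever is decided about OS[24], and the 24-month value can be read from the curve.
- The SAP has no such allowance for PFS rates (section 7.5.3.1), but those stop at 18 months, below expected minimum follow-up in all three scenarios (narrowly at HR 1.0). The contrast shows no inconsistency.
- Read literally, the two Protocol wordings could never be met once a subject was lost before month 24. The cutoff-based definition in SAP section 7.5.1.4 gives a sensible working meaning.
- The remedy is open to taste. Always reporting the rate would, at HR 1.0, put forward a landmark with 56% of subjects under 24 months of potential follow-up. Keeping the rule and adding a maturity criterion is equally defensible. Rewording the Protocol would also need an amendment (Protocol section 9.1.1).

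**Conclusion.** No change is needed. The plan pairs a 24-month minimum with an analysis expected at about 23 months (22.6 modelled at HR 0.72), and its SAP already allows for that case. What is left is an unspecified judgement about one descriptive rate that is not tested, so the type I error is untouched. Applied as written, the plan still yields valid Kaplan-Meier curves, and a valid OS[24] estimate if the rate is given. Reporting early costs about 0.01 point of standard error per arm at HR 0.72 and 0.23 point at HR 1.0 (2.93 − 2.70). Analysts would sensibly show the rate with its confidence interval and the numbers at risk.

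This rests on exponential survival, uniform 10-month accrual, no dropout unless stated, and censoring by entry date that is unrelated to prognosis. Longer accrual widens the shortfall; dropout, a longer control median or a cutoff about a month later narrows or closes it. None of these turns it into a matter that affects the trial's conclusion.

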8.5 Interim Analyses

Not applicable.

9 STUDY MANAGEMENT

9.1 Compliance

9.1.1 Compliance with the Protocol and Protocol Revisions

The investigator should not implement any deviation or change to the protocol without prior review and documented approval/favorable opinion of an amendment from the IRB/IEC (and if applicable, also by local health authority) except where necessary to eliminate an immediate hazard(s) to study subjects. If a deviation or change to a protocol is implemented to eliminate an immediate hazard(s) prior to obtaining relevant approval/favorable opinion(s), the deviation or change will be submitted as soon as possible to:

- IRB/IEC
- Regulatory Authority(ies), if applicable by local regulations per national requirements)

Documentation of approval/favorable opinion signed by the chairperson or designee of the IRB(s)/IEC(s) and if applicable, also by local health authority, must be sent to BMS. If an amendment substantially alters the study design or increases the potential risk to the subject: (1) the consent form must be revised and submitted to the IRB(s)/IEC(s) for review and approval/favorable opinion; (2) the revised form must be used to obtain consent from subjects currently enrolled in the study if they are affected by the amendment; and (3) the new form must be used to obtain consent from new subjects prior to enrollment.

If the revision is done via an administrative letter, investigators must inform their IRB(s)/IEC(s).

9.1.2 Monitoring

BMS or designee representatives will review data centrally to identify potential issues to determine a schedule of on-site visits for targeted review of study records.

Representatives of BMS must be allowed to visit all study site locations periodically to assess the data quality and study integrity. On site they will review study records and directly compare them with source documents, discuss the conduct of the study with the investigator, and verify that the facilities remain acceptable. Certain CRF pages and/or electronic files may serve as the source documents.

In addition, the study may be evaluated by BMS or designee internal auditors and government inspectors who must be allowed access to CRFs, source documents, other study files, and study facilities. BMS audit reports will be kept confidential.

The investigator must notify BMS promptly of any inspections scheduled by regulatory authorities, and promptly forward copies of inspection reports to BMS or designee.

9.1.2.1 Source Documentation

The Investigator is responsible for ensuring that the source data are accurate, legible, contemporaneous, original and attributable, whether the data are hand-written on paper or entered electronically. If source data are created (first entered), modified, maintained, archived, retrieved, or transmitted electronically via computerized systems (and/or any other kind of electronic devices) as part of regulated clinical trial activities, such systems must be compliant with all applicable laws and regulations governing use of electronic records and/or electronic signatures. Such systems may include, but are not limited to, electronic medical/health records (EMRs/EHRs), AE tracking/reporting, protocol required assessments, and/or drug accountability records).

When paper records from such systems are used in place of electronic format to perform regulated activities, such paper records should be certified copies. A certified copy consists of a copy of original information that has been verified, as indicated by a dated signature, as an exact copy having all of the same attributes and information as the original.

9.2 Records

9.2.1 Records Retention

The investigator (or head of study site in Japan) must retain all study records and source documents for the maximum period required by applicable regulations and guidelines, or institution procedures, or for the period specified by BMS, whichever is longer. The investigator (or head of study site in Japan) must contact BMS prior to destroying any records associated with the study.

BMS will notify the investigator (or head of study site in Japan) when the study records are no longer needed.

If the investigator withdraws from the study (eg, relocation, retirement), the records shall be transferred to a mutually agreed upon designee (eg, another investigator, IRB). Notice of such transfer will be given in writing to BMS.

9.2.2 Study Drug Records

Records for IP (whether supplied by BMS, its vendors, or the site) must substantiate IP integrity and traceability from receipt, preparation, administration, and through destruction or return. Records must be made available for review at the request of BMS/designee or a Health Authority.

If...	Then...
Supplied by BMS (or its vendors):	
 • Records or logs must comply with applicable regulations and guidelines and should include: • amount received and placed in storage area • amount currently in storage area • label identification number or batch number • amount dispensed to and returned by each subject, including unique subject identifiers • amount transferred to another area/site for dispensing or storage • nonstudy disposition (eg, lost, wasted)

If...	Then...
	
 • amount destroyed at study site, if applicable • amount returned to BMS • retain samples for bioavailability/bioequivalence, if applicable • dates and initials of person responsible for Investigational Product dispensing/accountability, as per the Delegation of Authority Form.

Sourced by site, and not supplied by BMS or its vendors (examples include IP sourced from the sites stock or commercial supply, or a specialty pharmacy)
	
The investigator or designee accepts responsibility for documenting traceability and study drug integrity in accordance with requirements applicable under law and the SOPs/standards of the sourcing pharmacy.
 
These records should include:
 
 • label identification number or batch number • amount dispensed to and returned by each subject, including unique subject identifiers • dates and initials of person responsible for Investigational Product dispensing/accountability, as per the Delegation of Authority Form.

BMS or designee will provide forms to facilitate inventory control if the investigational site does not have an established system that meets these requirements.

